## SPECIFIC AIMS

Systemic inflammation caused by exposure to cardiopulmonary bypass or other conditions such as sepsis, ischemia-reperfusion, trauma, major surgery and prolonged hyperglycemia leads to endothelial activation by circulating cytokines and subsequent injury to glycocalyx and endothelium.[\[1, 2\]](#) Intravascular solutions used for plasma volume replacement, such as human albumin 5%, demonstrate endothelial protective effects which may mitigate the postoperative inflammatory response and consequent endothelial injury.[\[3, 4\]](#) Administration of hydroxyethyl starch (HES) solutions, which have known adverse effects on endothelial function, increases mortality and kidney injury in patients with sepsis [\[5, 6\]](#) perhaps due to aggravation of endothelial and glycocalyceal injury.[\[7-9\]](#) Whether endothelial function is improved in cardiac surgical patients receiving plasma volume resuscitation with 5% human albumin compared with HES solutions, however, is unknown. Our proposed investigation will *test the primary hypothesis* that **postoperative endothelial function**, measured with peripheral arterial tonometry as reactive hyperemia index (RHI) within 2 hours following surgery, **is improved in cardiac surgical patients who are randomized to receive human albumin for plasma volume replacement**, compared with 6% HES solutions. Secondarily, we *hypothesize* that **patients who receive 5% human albumin will have reduced plasma concentrations of molecular biomarkers of glycocalyceal injury (syndecan 1 and endocan)** compared with those who receive 6% HES solutions. *If plasma volume resuscitation with 5% human albumin preserves perioperative endothelial function, kidney dysfunction and other organ injury following cardiac surgery may be reduced.*

**Specific aim 1. To determine whether human albumin 5% improves postoperative endothelial function compared with 6% HES (130/0.4).** Endothelial function will be assessed 2 hours following surgery by measuring RHI using peripheral arterial tonometry (EndoPAT, Itamar Medical Inc., Caesarea, Israel), a well validated tool used in endothelial dysfunction diagnostics and cardiovascular risk stratification.[\[10-12\]](#) We *hypothesize* that patients who receive human albumin 5% for intravascular volume replacement during surgery will have improved endothelial function at 2 hours following surgery compared with those who receive 6% HES (130/0.4).

**Sub-aim 1.** Our preliminary data suggest that post-operative endothelial function is poorly correlated with baseline (preoperative) endothelial function. In a subset of patients, we will describe the expected changes that occur in endothelial function during the perioperative period (baseline, early postoperative, 24 hours postoperative). We will assess this for 40 patients (20 per group), at baseline, within 2 hours after surgery, and 24 hours after surgery. We *hypothesize* that there will be a decline in endothelial function from baseline to 2 hours after surgery and no significant difference in function between baseline and at 24 hours after surgery.

**Specific aim 2. To determine whether human albumin 5% reduces plasma biomarkers of endothelial and glycocalyceal damage.** We will measure plasma concentrations of syndecan 1 and endocan at baseline (before surgery), and 1 and 24 hours following surgery. Syndecan 1 and endocan are components of glycocalyx, and increased blood concentrations of these molecules indicate glycocalyceal shedding and endothelial dysfunction.[\[13, 14\]](#) We *hypothesize* that patients who receive human albumin 5% for intravascular volume replacement during surgery will have reduced concentrations of syndecan 1 and endocan at 1 and 24 hours following surgery compared with those who receive 6% HES (130/0.4).

## BACKGROUND AND SIGNIFICANCE

### Inflammation causes endothelial injury and degradation of the glycocalyx

The vascular endothelium and its proteinaceous coating, the glycocalyx, is omnipresent throughout the circulatory system and plays a key role in preserving vascular integrity and function. The endothelium regulates vascular tone, inhibits intravascular thrombosis and modulates the inflammatory response by modifying the adhesion/migration of leukocytes and other mediators.[\[8, 14-17\]](#) During inflammation induced by cardiopulmonary bypass or sepsis, leukocytes and other inflammatory mediators target the endothelium and glycocalyx causing disruption of vascular endothelial function. Vascular permeability, leukocyte trafficking, and oxidative stress are increased, while vascular tone is reduced. Oxygen and nutrient delivery to cells is impaired and a procoagulant state is promoted.[\[1, 2, 16, 18\]](#)

Leukocyte activation and endothelial adherence contribute to microvascular flow impairment. Vascular hyperpermeability and albuminuria occur, and microthrombi form in the kidney and other organs.[\[19-22\]](#)

### **Human albumin 5% has beneficial effects on endothelial and glycocalyceal function compared with HES solutions**

Human albumin has demonstrated beneficial effects on vascular endothelial and glycocalyceal function in ex vivo models. It prevents fluid extravasation more effectively compared with crystalloid or synthetic HES solutions in an ex vivo heart model, and has been shown to inhibit binding of activated polymorphonuclear leukocytes to bovine aortic endothelial cells. [\[3\]](#) [\[4\]](#) Shear stress-mediated nitric oxide release and coronary vasodilatation is potentiated with administration of human albumin compared with HES solutions.[\[9\]](#) Further, binding of neutrophil-derived myeloperoxidase to bovine aortic endothelial cells, a mediator of multiple oxidative and nitric oxide-consuming reactions, is inhibited by human serum albumin, while it is amplified by HES solutions.[\[4\]](#) Thus the protective characteristics of plasma volume administration with human albumin may reduce endothelial injury in the kidney and other organs, and, ultimately, reduce postoperative organ dysfunction in cardiac surgical patients, especially compared with use of HES solutions.

### **Endothelial function can be assessed by validated noninvasive techniques**

Endothelial function is measured by the magnitude of arterial dilation that occurs following the release of nitric oxide or other endothelium-derived vasoactive substance.[\[23\]](#) Brachial flow-mediated dilation (FMD), a standard measure of endothelial function,[\[24\]](#) is a noninvasive ultrasound-based method that measures the increase in arterial diameter caused by shear stress-mediated endothelial release of nitric oxide. FMD is closely correlated with invasive measures of endothelial function;[\[25\]](#) however, it is technically demanding, affected by the cardiac cycle, and dependent upon the quality of ultrasound images.[\[24\]](#) Peripheral arterial tonometry (PAT) is a sensitive, accurate, and reproducible noninvasive measure of endothelial function. PAT measures endothelium-mediated changes in vascular tone using beat-to-beat plethysmographic recordings of the finger pulse wave amplitude with pneumatic probes at baseline and following release of a 5-min occlusion of the brachial artery (using a standard blood pressure cuff). The endothelium-dependent flow mediated dilation response is manifested as reactive hyperemia which is quantified by the post-occlusion to pre-occlusion ratio. PAT correlates closely with FMD assessed with brachial arterial ultrasound.[\[12\]](#) Use of PAT in patients after cardiac surgery provides a noninvasive reliable and reproducible measure of systemic endothelial function.

### **Endothelial function can be measured by biomarkers in the blood**

Plasma concentration of syndecan 1 serves as a biomarker of endothelial injury and glycocalyx degradation and correlates with serum levels of inflammatory cytokines and mortality in trauma patients.[\[13\]](#) Endocan is another component of the glycocalyx which is released during inflammation in response to tumor necrosis factor- $\alpha$  (TNF- $\alpha$ ) and interleukin-1 (IL-1), and correlates with severity of sepsis.[\[14\]](#) Assessment of plasma concentrations of syndecan 1 and endocan provide quantifiable measures of perioperative endothelial injury and glycocalyceal disruption.

[figure not shown]
## **SIGNIFICANCE**

Perioperative inflammation and endothelial dysfunction lead to multi-organ system dysfunction following cardiac surgery, including postoperative kidney injury, pulmonary insufficiency, coagulopathy, vasoplegia, hemodynamic instability, and postoperative delirium. Determining whether plasma volume resuscitation with 5% human albumin reduces perioperative endothelial/glycocalyceal dysfunction compared with 6% HES solutions will 1) improve our understanding of the clinical effects of volume replacement solutions, 2) provide evidence to support a mechanism of perioperative and sepsis-associated kidney injury associated with HES solutions, 3) identify potential targets for therapeutic intervention and aid in the development of novel strategies to reduce perioperative and sepsis-induced kidney and other organ injury, 4) contribute to our ultimate goal of reducing postoperative morbidity and mortality in patients who require cardiac surgery.

## EXPERIMENTAL METHODS AND DATA ANALYSIS

### Research Design and Methods

This investigation will represent a substudy of a current ongoing clinical trial (SHARP: Voluven vs. Albumin comparing effect of 5% human albumin vs. 6% HES (130/0.4) on postoperative kidney function and coagulation. Patients who consent for SHARP study will be invited for participation in this substudy of endothelial/glycocalyceal function.

**Inclusion criteria:** Patients aged 40 – 85 years old who signed a written, informed consent for participation in this investigation, scheduled for elective aortic valve replacement with or without coronary artery bypass grafting involving nonpulsatile cardiopulmonary bypass, with or without additional minor surgical procedure.

**Exclusion criteria:** Patients with Raynaud's disease or other disease associated with upper extremity vascular insufficiency, and inability to perform EndoPAT exam (inability to lie still for 15 min, or significant finger deformity), patients meeting SHARP exclusion criteria (renal failure with oliguria or anuria not related to hypovolemia, dialysis, preoperative creatinine > 1.6 mg/dL, anticipated deep hypothermic circulatory arrest, known hypersensitivity or allergy to HES, clinical conditions with volume overload e.g., patients in pulmonary edema or congestive heart failure, severe hypernatremia or severe hyperchloremia, intracranial bleeding, pregnant or breast feeding women, critically ill adult patients e.g. patients who are hospitalized in the intensive care unit prior to surgery, severe liver disease, pre-existing coagulopathy).

### Randomization

Patients will be randomized to receive either HES 130/0.4 (Voluven) or albumin 5% for treatment of intraoperative acute hypovolemia. (Treatment assignments will be generated using a reproducible algorithm in the PLAN procedure in SAS statistical software. Randomization will be conducted using an existing password-protected web randomization site used for all clinical trials coordinated by the Department of Outcomes Research and maintained by the Anesthesia Institute statistical team.)

### Outcomes

Primary outcome is postoperative endothelial function measured by Reactive Hyperemia Index (RHI) using a peripheral arterial tonometer (EndoPAT, Itamar Medical Inc., Caesarea, Israel) within 2 hours following completion of surgery. A subset of patients will also have RHI measured at baseline and 24 hours after surgery.

Secondary outcomes will include blood biomarkers indicative of endothelial/glycocalyceal injury including plasma concentrations of syndecan 1 and endocan measured at baseline (after arterial line

placement), within one hour ( $\pm 1$  hour) of ICU arrival, and 24 hours ( $\pm 2$  hours) following completion of surgery (or within 2 hours prior to ICU discharge if patient is discharged in less than 24 hours).

### **Experimental Protocol**

Cardiac surgical patients enrolled in the SHARP study will be randomized to either 5% human albumin or 6% HES on entrance to the operating room. Anesthetic and Surgical management will follow protocol established by SHARP study including administration of a blinded study solution which contains 5% human albumin or 6% HES following separation from cardiopulmonary bypass. Blood will be collected for measurement of baseline syndecan 1 and endocan following arterial line and urinary catheter placement. At 1 and 24 hours following surgery completion, blood will be collected for measurement of syndecan 1 and endocan. Within two hours of ICU arrival, PAT will be performed in ICU. In a subset of patients, PAT will be performed preoperatively and at 24 hours after surgery.

Because vasoactive substances may influence EndoPAT measurement, we will collect data on use of all preoperative antihypertensive medications that have direct or indirect effect on smooth muscle relaxation. Cardiac surgery patients often need intraoperative and postoperative inotropic support. Data on use of perioperative vasoactive medications that may influence EndoPAT results including epinephrine, norepinephrine, vasopressin, milrinone, nitroglycerine, nitroprusside, and sedatives such as propofol, dexmedetomidine and others will be recorded and subsequently adjusted for in the analysis. Data on transfusion of packed red blood cells and blood components will be collected from Anesthesia Record Keeping System. Minimum hematocrit (HCT) will be approximately 23% following cardiopulmonary bypass and 21% on cardiopulmonary bypass. Packed blood cell, platelets, fresh frozen plasma and/or cryoprecipitate transfusions may be administered as determined necessary by attending anesthesiologist or surgeon. Any imbalance in blood product transfusion between the two study groups will be adjusted for in analysis.

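### Transfusion imbalance and perioperative drugs are to be adjusted for with no cut-off at randomisation or study fluid, so the primary RHI model can condition on a consequence of the assigned fluid

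*Combined protocol and SAP*

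**What the plan says.** All references are to the combined protocol and SAP.

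- **Timing (Experimental Protocol).** Patients "will be randomized to either 5% human albumin or 6% HES on entrance to the operating room". Management then includes "administration of a blinded study solution which contains 5% human albumin or 6% HES following separation from cardiopulmonary bypass".
- **Transfusion (Experimental Protocol).** "Any imbalance in blood product transfusion between the two study groups will be adjusted for in analysis". No time limit and no model are given.
- **Drugs (Experimental Protocol).** Epinephrine, "norepinephrine, vasopressin, milrinone, nitroglycerine, nitroprusside, and sedatives such as propofol, dexmedetomidine and others will be recorded and subsequently adjusted for in the analysis". The stated reason is "Because vasoactive substances may influence EndoPAT measurement". The section refers to inotropic support both during and after the operation.
- **Statistical analysis.** Baseline and procedural variables are screened, and any with an absolute standardised difference (ASD) above 0.25 is adjusted for in the analyses that follow. The substudy is called modified intent-to-treat.
- **Primary analysis.** RHI is compared by linear regression, adjusted for imbalanced characteristics of the patient and of the procedure.
- **Secondary analyses.** The biomarker models name only baseline biomarkers and imbalanced baseline variables.
- **Target (Specific Aims).** The hypothesis is that postoperative endothelial function "is improved in cardiac surgical patients who are randomized to receive human albumin for plasma volume replacement".

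**The concern.** The hypothesis and the modified intent-to-treat label both point to the effect of being assigned albumin rather than HES. Adjusting for something the assigned fluid has changed estimates a different quantity.

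The transfusion rule is the clearest case. Once study fluid has been given, a difference in transfusion between arms is either chance or an effect of the fluid, and the rule adjusts for it either way. A real fluid effect also makes the rule more likely to apply.

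The documents make such an effect plausible. The parent trial is described as "comparing effect of 5% human albumin vs. 6% HES (130/0.4) on postoperative kidney function and coagulation", and the Significance section states: "Perioperative inflammation and endothelial dysfunction lead to multi-organ system dysfunction following cardiac surgery, including postoperative kidney injury, pulmonary insufficiency, coagulopathy, vasoplegia, hemodynamic instability".

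At stake is what the primary RHI estimate means. Two statisticians following this text could fit different primary models.

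**Working it through.** **1. Does another section close the gap?** The Experimental Protocol rules name no model and no cut-off. Statistical analysis and Primary analysis admit procedural variables, which does not exclude transfusion or intraoperative drugs. Only Secondary analyses says baseline. Even there, the Experimental Protocol wording is not specific to RHI, and the ASD rule covers all the analyses that follow it. No between-arm RHI analysis free of these variables is guaranteed: the Wilcoxon test is used only if transformations fail, and the paired t-tests compare times within patients. The gap stands.

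**2. The plan's own power.** Inputs from Sample size analysis: 85 patients, SD 1.4, alpha 0.05, differences 1.0 and 0.73. Assumed: 42 against 43 patients, two-sided test.

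SE = 1.4 × √(1/42 + 1/43) = 0.304. The noncentral t gives 90.2% power for 1.0 and 66.1% for 0.73, against the plan's 90% and 65%. The plan's figures reproduce.

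**3. Illustration of bias.** The documents give no covariate effects, so these inputs are assumptions: one continuous covariate M with within-arm SD 1, a within-arm correlation ρ with RHI of -0.1, -0.3 or -0.5, and a fluid effect on M (the shift) of 0.25 or 0.5 SD in either direction. M lies on the path from fluid to RHI, and nothing else confounds M and RHI.

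*Always adjusted (the drug wording).* Mean estimate = 0.73 - ρ × 1.4 × shift. For example, with ρ = -0.5 and shift = -0.5: 0.73 - 0.35 = 0.38.

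| ρ | Albumin lowers M by 0.25 / 0.5 SD | Albumin raises M by 0.25 / 0.5 SD |
|---|---|---|
| -0.1 | 0.70 / 0.66 | 0.77 / 0.80 |
| -0.3 | 0.63 / 0.52 | 0.84 / 0.94 |
| -0.5 | 0.56 / 0.38 | 0.91 / 1.08 |

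The bias runs from 0.035 to 0.35. That is 0.035/0.73 = 5% to 0.35/0.73 = 48% of the effect, or 0.12 to 1.15 standard errors. With no shift it is zero.

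*Adjusted only when ASD > 0.25 (transfusion, if the plan's ASD rule defines imbalance).* The rule applies in 25% of trials with no shift, 51% at 0.25 SD and 88% at 0.5 SD (noncentral t). Simulated mean estimates, 40,000 trials per cell:

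| ρ | Albumin lowers M by 0.25 / 0.5 SD | Albumin raises M by 0.25 / 0.5 SD |
|---|---|---|
| -0.1 | 0.70 / 0.67 | 0.76 / 0.80 |
| -0.3 | 0.64 / 0.53 | 0.82 / 0.93 |
| -0.5 | 0.58 / 0.39 | 0.88 / 1.07 |

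**4. Zero total effect.** Under the triggered rule the 5% test rejects in about 5% / 6% of trials (ρ = -0.1, shift 0.25 / 0.5), 6% / 10% (-0.3) and 7% / 23% (-0.5). In this model a zero total effect with a non-zero shift requires a direct fluid effect that cancels the mediated one. In the last cell it is 0.5 × 1.4 × 0.5 = 0.35.

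**5. Precision given up.** With no shift, adjustment reduces the residual SD to 1.4 × √(1 - ρ²) = 1.39, 1.34 or 1.21. Simulated power for 0.73 is then 66%, 69% or 78%, against 66% unadjusted.

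**The case against.** - **No documented mechanism.** No section says that the fluid changes pressor use, sedation or transfusion. Coagulation appears only as a parent-trial outcome, and coagulopathy and vasoplegia are linked to inflammation and endothelial dysfunction, not to the fluid. This stands. It limits the point to what the rule permits.
- **The statistical sections may govern.** Experimental Protocol is an operational section, and the later sections can be read as leaving post-fluid variables out. That reading is possible, but the text does not settle it, and the transfusion sentence is a stated rule.
- **The drug adjustment has a purpose.** If these drugs distort the EndoPAT reading, an unadjusted contrast carries the artefact. This stands too. A reader might infer that drug adjustment is simply an error and must go. The documents do not support that, because it is a trade-off between estimands. Adjustment removes the artefact only under assumptions the plan does not state, such as no unmeasured common cause of drug use and RHI. No measurement reason is given for transfusion.
- **Some later variables are harmless.** On the timing in Experimental Protocol, bypass-phase variables precede study fluid and cannot be changed by it, so a strict cut-off at randomisation would discard them needlessly. The fix allows for this.
- **Assumed inputs.** The correlations and shifts have no source in the documents, and real drug or transfusion data may be binary or skewed. The extreme cells are corners, not forecasts.

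**Conclusion.** The point holds as a fault in the stated adjustment rules and should be fixed. Confidence is high that the wording lets post-fluid transfusion and drugs into the primary RHI model. It does not extend to bias actually occurring.

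A reader might infer that the primary result will be biased. The documents do not support that: the sign and size are unknown, and the bias is nil if the fluid does not shift the variable. A reader might also take the 23% as ordinary type I error inflation. It is an error only relative to a zero total effect, since that scenario contains a real direct effect of 0.35 that the adjusted model partly detects.

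The conclusion rests on the effect of assignment being the target, as Specific Aims and the modified intent-to-treat label indicate. The numerical ranges rest on the assumed single-covariate model.

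**What to change.** 1. Delete the transfusion-imbalance adjustment from the primary RHI model.
2. State that the ASD > 0.25 rule covers only variables fixed before study fluid can act. These are pre-randomisation variables, or pre-fluid procedural ones once the timing is reconciled: Randomization speaks of fluid for acute hypovolaemia during the operation, while Experimental Protocol places it after separation from bypass.
3. Apply the same limit to the biomarker models. Their baseline biomarker covariates can stay.
4. Report transfusion, vasoactive drug and sedative use by arm.
5. Guarantee a between-arm RHI model without post-fluid drugs. Show the drug-adjusted model beside it as a labelled analysis with its assumptions. The sponsor should state in advance which is primary.
6. Bring Experimental Protocol, Statistical analysis, Primary analysis and Secondary analyses into agreement.

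The cost is SAP wording. The drug and transfusion data are already to be collected, and the sample size does not change. A cut-off at randomisation needs no administration times; a pre-fluid cut-off needs times relative to first study fluid. There are two downsides. Some precision is lost if the fluid does not affect these variables (the 66% against 66% to 78% shown above), and the estimate without drug adjustment includes any drug-related measurement artefact.

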### **Data Management**

Study Personnel will record data on Case Report Forms. Case report forms will be kept in a locked storage room with access limited to study personnel. Data from Case report forms will be inputted into the study database in REDCap for Data collection and storage. REDCap is a mature, secure web application for building and managing online surveys and databases. The REDCap application allows users to build and manage online surveys and databases quickly and securely, and is currently in production use or development build-status for more than 244,000 projects with over 335,000 users spanning numerous research focus areas across the consortium.

